Study Aims	
The human component of the study has two aims:
 
Aim 1. Identify the pathology, structural cell profile (airway fibroblast and epithelial cell) and redox status corresponding to regional areas of fixed and reversible post-bronchodilator defects (BD) in obese asthmatics.
 
Aim 2. Define the cellular requirement for redox-mediated TGF-β signaling between airway epithelial cells and fibroblasts driving regional remodeling in obese asthma.

Number of Subjects	
Targeted enrollment number - 50
 
Enrollment will consist of approximately:
 
• 15-20 “Early Onset T2 high obese” asthma patients (diagnosed at age < 12 years, and FeNO\geq25 ppb)• 15-20 “Late onset obese, non T2” asthma (diagnosed at age \geq12 years, FeNO < 25ppb, obese (BMI\geq30kg/m²) patients will be enrolled• 10 non-asthma obese controls who demonstrate no evidence of atopy or bronchodilator responsiveness will be also be enrolled 
Recruitment will include adults (18-65 years old) with physician-diagnosed asthma

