Subject Recruitment and Screening: We anticipate 40 early and late onset obese asthma patients and 10 obese non-asthma volunteers will undergo Hyperpolarized $^{129}\text{XeMRI}$ and bronchoscopy after screening over the course of this study. Patients will undergo, twice in succession, an approximately 30-min MRI protocol, consisting of several breath-hold scans after hyperpolarized ^{129}Xe or room air administration. The imaging will be repeated pre- and post-bronchodilator (BD), thus requiring 60-min to complete. The results of a co-registered CT of the chest and the pre-post bronchodilator Hyperpolarized $^{129}\text{XeMRI}$ will be reviewed by the Duke Imaging Team to identify segmental persistent post-BD ventilatory defects in obese asthmatics. The CT will provide precise structural information for segmental delineation, while MRI informs regional ventilatory function, interstitial uptake and lung microstructure and function. For these purposes, we need a single high-res (standard dose) CT scan at full inspiration. The Duke Imaging Team will dictate to the bronchoscopist in a blinded fashion which segments contain BD fixed and BD reversible ventilatory defects. Bronchoalveolar lavage (BAL), endobronchial biopsies and brushings will be obtained from these segments.

Study participants will be enrolled at the Duke University Health System from clinics, hospitals and communities via various IRB-approved recruitment methods, including Protocol Pro00102890; Pulmonary Medicine Healthy Volunteer Data Repository (HVDR) and Pro00103507; Pulmonary Medicine Lung Disease Volunteer Data Repository (LDVDR).

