- **Bronchoscopy with Bronchial alveolar lavage and Biopsy**

Bronchoscopy is an established clinical procedure that has been used as standard for diagnosis of lung lesions. Overall, research bronchoscopy in adult asthmatics is considered to be a safe and well-tolerated procedure⁴⁷. Furthermore, bronchoscopy with bronchoalveolar lavage, endobronchial biopsies and airway brushings have been extensively used as clinical research tools in the last decade with complication rates not more than 2-3%.

The Imaging Team will dictate in a blinded fashion to the bronchoscopist where the samples will be obtained based on the results of the co-registered CT and pre-post bronchodilator ¹²⁹XeMRI ventilation images. Samples will be obtained from lung segments containing bronchodilator fixed and bronchodilator reversible defects in the following order to ensure standardization: 1) bronchial brushings, 2) bronchoalveolar lavage (BAL), 3) endobronchial biopsies.

- **Bronchoalveolar Lavage:** The purpose of the BAL is to evaluate the inflammatory cell profile. ¹²⁹XeMRI images will be used to guide where the bronchoscope will be placed and wedged for BAL collection. Three 40 ml aliquots of 37°C sterile 0.9% saline solution are instilled after the bronchoscope is wedged into each subsegment. The bath water temperature is continuously measured. The BAL fluid is harvested by immediate gently hand suction applied to each instilling syringe. Syringes are placed immediately in ice. The volume of the effluent is measured after the procedure and samples are combined with the exception of the first aliquot return which represents the “bronchial” portion of the lavage⁴⁸. Reduction in oxygen saturation following bronchoalveolar lavage is common for several hours. Supplemental O₂ will be administered as required. Our standard method will be used to count and differentiate cell types in the airway and alveolar fraction of the BAL^{49 50 51}.
 - 120 mL instilled in BD reversible and 120 mL instilled in BD fixed airways

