DATA ANALYSIS & STATISTICAL CONSIDERATIONS: For the *ex vivo* studies, conditions will be performed in triplicate and experiments will be independently replicated to ensure reproducibility. For the *in vivo* assessments of airway remodeling and fibrosis (bronchodilator reversibility on ¹²⁹XeMRI), we will compare biomarkers of fibrosis (e.g., trichrome or percent elastic fiber staining) between BD types (fixed and reversible airway segments) both within and between obese asthma groups (early onset, late onset and non-asthma control) using a repeated measures two-way ANOVA with appropriate distributional assumption. Main effects of BD type, obese asthma group and their interaction will be evaluated with repeating BD type within subject (random effect) with compound symmetry variance structure. If significant main effect differences are found, pairwise comparisons between BD types and obese asthma groups will be done using Tukey's post-hoc test. Assuming a 50% decrease in fibrosis between BD fixed and reversible types, a sample size of 10 per group provides our study with ≥80% power to detect an effect size of 0.53 within and 0.60 between groups, where effect size (*f*) is the size of the mean differences relative to the standard deviation and assumed correlation (*p*) within group of 0.30. A p-value <0.05 will be considered statistically significant and all analyses will be performed using SAS version 9.4 or higher (SAS Institute, Inc., Cary, NC). Blinding to conditions and tissue sources will occur across the experimental design. In particular, tissues samples (post-BD fixed and BD reversible tissue based on region) will be blinded to the individual performing the experiments and the individual assays. The key for the tissue samples will be maintained by the program statistician and un-blinding will occur during data analysis by the statistician.

Because of [name] conflict of interest related to ¹²⁹XeMRI, and as required by his Polarean management plan, data analysis and image analysis will be conducted by un-conflicted individuals.

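### The fixed-versus-reversible tests include non-asthma controls, who may often lack one defect type, and the plan gives no sampling, labelling or model rule for that case

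*Combined protocol and SAP*

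**What the plan says.** DATA ANALYSIS & STATISTICAL CONSIDERATIONS, and the synopsis under Statistical Methodology, specify a repeated-measures two-way ANOVA that compares fibrosis markers "between BD types (fixed and reversible airway segments) both within and between obese asthma groups (early onset, late onset and non-asthma control"). "Main effects of BD type, obese asthma group and their interaction will be evaluated with repeating BD type within subject", with compound symmetry. On follow-up: "If significant main effect differences are found, pairwise comparisons between BD types and obese asthma groups will be done", by Tukey's method. The threshold is "A p-value <0.05 will be considered statistically significant". The power statement is "a sample size of 10 per group provides our study with ≥80% power" for effect sizes of 0.53 within and 0.60 between groups, with a correlation of 0.30.

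The synopsis (Number of Subjects) plans 15–20 participants in each asthma group and "10 non-asthma obese controls who demonstrate no evidence of atopy or bronchodilator responsiveness". Subject Recruitment and Screening gives 40 asthma patients and 10 controls. Both sets of control criteria require FEV1 above 80% of predicted, FEV1/FVC above the lower limit of normal, and negative methacholine and oscillometry tests. The synopsis also excludes a control with an FEV1 bronchodilator response of 12% or more; the exclusion list in the body does not.

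Every participant has bronchoscopy. The image review is done "to identify segmental persistent post-BD ventilatory defects in obese asthmatics", and the bronchoscopy description says "Samples will be obtained from lung segments containing bronchodilator fixed and bronchodilator reversible defects".

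**The concern.** The BD-type factor is crossed with a group for which the question is not asked. Aim 1 and the first primary outcome concern fixed and reversible defects in obese asthmatics, so a BD-type effect averaged over three groups is not the quantity the aim names.

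The control criteria also make a bronchodilator-reversible defect less likely. No eligibility criterion, for any group, requires either defect type. No section says which segment is used when one type is absent, what label that tissue carries, or how the participant enters the model. The missing-at-random statement in the synopsis does not help, because a segment that does not exist is not a missing observation.

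Two outcomes are possible, and they differ:

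- **No reversible segment in controls.** That cell is empty and the three-group marginal BD contrast cannot be estimated.
- **Controls sampled and labelled anyway, with little true difference.** The main effect is diluted, and the pairwise tests depend on a significant main effect. The interaction has 2 degrees of freedom and can be significant because asthma differs from control, with no difference between early and late onset.

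The sampling site and its label cannot be recovered after bronchoscopy.

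**Working it through.** **1. Reproduce the printed figures** (noncentral F, alpha 0.05, 3 × 10 = 30 participants).

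- Between: λ = f²N = 0.60² × 30 = 10.80 on (2, 27) df; power 80.0%.
- Within: λ = 0.53² × 30 = 8.427 on (1, 27) df; power 79.9% (80.0% on 28 df).

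So the printed 0.53 appears to count 10 control pairs, to act as mean difference ÷ SD of the paired differences, and to leave the correlation unused. Call this reading A.

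Reading B uses the correlation. With two levels the mean difference is 2f = 1.06 SD, and the variance of a paired difference is 2(1 − 0.30) = 1.4 SD². At 10/10/10, λ = 0.53² × 30 × 2/(1 − 0.30) = 24.08 and power is 99.7%. The claim of at least 80% then holds, but 0.53 is not its threshold, which would be about 0.31.

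**2. BD-type main effect with a zero control difference** (an assumption). Let d be the difference in both asthma groups and s² the variance of a paired difference. The equally weighted mean is (d + d + 0)/3 = 2d/3.

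- Three groups: λ = 4d² ÷ [s²(1/n₁ + 1/n₂ + 1/n₃)] on N − 3 df.
- Asthma only: λ = 4d² ÷ [s²(1/n₁ + 1/n₂)] on n₁ + n₂ − 2 df.

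The numerators are equal, so null controls only add the term 1/n₃ to the variance.

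| Reading | n | Three-group λ | Power | Asthma-only λ | Power |
|---|---|---|---|---|---|
| A (d = 0.53, s² = 1) | 15/15/10 | 1.1236/0.2333 = 4.815 | 57% | 1.1236/0.1333 = 8.427 | 80% |
| A | 20/20/10 | 1.1236/0.2 = 5.618 | 64% | 1.1236/0.1 = 11.236 | 90% |
| B (d = 1.06, s² = 1.4) | 15/15/10 | 4.4944/0.3267 = 13.76 | 95% | 4.4944/0.1867 = 24.08 | 99.7% |
| B | 20/20/10 | 4.4944/0.28 = 16.05 | 98% | 4.4944/0.14 = 32.10 | >99.9% |

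**3. Other control differences, reading A.** If the control difference is half the asthma difference, the mean is 2.5d/3 and λ = 6.25d² ÷ Σ(1/n). This gives 7.52 and 8.78, with power 76% and 83%. If controls share the full difference, λ = 9d² ÷ Σ(1/n) = 10.84 and 12.64, with power 89% and 94%. Against 80% and 90% in asthma alone, including controls helps only when they show nearly the same difference.

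**4. Interaction when the asthma groups are identical and the control difference is zero.** λ = (d²/s²) × n_a n_c/(n_a + n_c) on (2, N − 3) df, where n_a is all asthma participants and n_c the controls.

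- 15/15/10: factor 30 × 10/40 = 7.5. λ = 2.107 (A) and 6.019 (B); rejection 22% and 55%.
- 20/20/10: factor 40 × 10/50 = 8. λ = 2.247 (A) and 6.421 (B); rejection 24% and 59%.

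The asthma-only interaction rejects 5% of the time in this case.

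**5. Empty control-reversible cell.** A contrast free of the group effect must give the lone control-fixed cell zero weight. The BD-type test then rests on the asthma groups, and the interaction falls to 1 df (early versus late). Steps 2 to 4 do not apply; the harm is that three-group marginal means are not estimable.

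**6. Detectable effect for asthma pairs, reading A, 80% power.** 0.53 at 15/15 and about 0.455 at 20/20.

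**The case against.** A reader might infer that the control cells will be empty or filled with meaningless labels. The documents do not show that. The control criteria rest on spirometry, bronchodilator response, methacholine and oscillometry, none of which is a regional image. The background itself says that global lung-function measures miss regional change, and it reports MRI defects in people with normal spirometry, although only in asthmatics. Controls are also obese. No MRI defect frequency is given for them, so a zero control difference is an assumption.

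A reader might also infer that dilution leaves the study underpowered. On reading B it does not: three-group power stays at 95–98% at the planned enrolment. The two-thirds figure also needs equal weighting of the groups and every control labelled.

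Nor does the plan say that it would read a significant interaction as a difference between early and late onset. Controls are a named level of the factor, an interaction driven by them is a legitimate result, and within-group contrasts would show where it lies. But the text ties pairwise tests to significant main effects and describes no follow-up of the interaction, so the ambiguity remains.

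Finally, an asthma-only model is not the only remedy. Prespecified asthma contrasts within the three-group model serve as well, and a control with a real defect bears on the central hypothesis about sites of abnormal ventilation and should not be discarded. These objections limit the size of the concern. They do not supply the missing rules or make the three-group average the quantity that Aim 1 names.

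**Conclusion.** The concern holds as a mismatch between the test and the aim, together with a missing rule for participants who lack one defect type. It should be fixed; confidence is moderate.

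The size is conditional. Under a zero control difference and equal weights, the loss in BD-type power is 23 to 26 percentage points on reading A (80 − 57 and 90 − 64) and about 5 points or less on reading B. The excess interaction rejection is material on both readings. If the control-reversible cell is wholly empty, the issue is estimability and none of these losses applies. How often controls lack a reversible defect cannot be settled from the documents.

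**What to change.** 1. Make the primary BD-type and BD-type-by-onset tests a 2 × 2 analysis of the two asthma groups, or the equivalent prespecified asthma-only contrasts in the three-group model.
2. Compare control tissue with asthma-fixed and with asthma-reversible tissue as two separate between-person contrasts.
3. Label control tissue by its actual MRI status, with no defect as a category. Keep any control with real defects in a secondary analysis.
4. State, for every group, which segment is sampled when a participant has only one defect type or none, and how that participant enters the model.
5. Restate within-person power for asthma pairs and say which definition of f is used and whether the correlation of 0.30 enters. On the plan's apparent formula the detectable effect is 0.53 at 15/15 and about 0.455 at 20/20.

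The cost is wording: a rewritten power sentence, a changed model paragraph and a sampling rule settled before further bronchoscopies. No patients or procedures are added. The price is that controls no longer count toward the BD-type test, which gives up some power if they do share nearly the full asthma difference.

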--	---

Inclusion/Exclusion Criteria for Non-asthmatic controls
	
INCLUSION
 
 1. No history of asthma or other chronic lung diseases 2. Male and female patients, 18 - 65 years old, inclusive 3. Not currently smoking or using other forms of tobacco-related products (including vaping) 4. Smoking history <10 pack years and no smoking in the past 3 months 5. FEV1 > 80% of predicted and FEV1/FVC > lower limit of normal. 6. Ability to sign consent 7. BMI \geq 30 kg/m² 8. Negative Methacholine challenge (historical results from previous studies or documented in clinical records within preceding year are acceptable alternatives) and negative PD40 to X5 and R5 on IOS 
EXCLUSION
 
 9. Respiratory tract infection within the 4 weeks prior to Visit 0 10. Oral or systemic corticosteroid burst (for any indication) within the 4 weeks prior to Visit 0 11. One-time doses, such as intra-articular injections into a shoulder or knee joint, require a 4-week washout prior to Visit 0 12. Significant concomitant medical illness, including (but not limited to) heart disease, cancer, uncontrolled diabetes, other chronic lung diseases 13. Chronic renal failure (creatinine > 2.0) at Visit 0 14. Positive urine pregnancy test at Visit 0 or at any time during the study 15. Untreated sleep apnea 16. Participation in an intervention study (including bronchoscopy) or use of investigative drugs within the past 30 days or plans to enroll in such a trial during the study 17. Unable or unlikely to complete study assessments in the opinion of the Investigator 18. Study intervention poses undue risk to patient in the opinion of the Investigator 19. Positive Methacholine challenge- Confirmation of asthma: Either (1) 12% or greater bronchodilator response (BDR) in FEV1 to albuterol at Visit 0 OR (2) PC20 methacholine \leq 16 mg/ml at Visit 0 (historical results from previous studies or documented in clinical records within preceding year are acceptable alternatives) 
AND/OR Positive PD40 to X5 and R5 on IOS.

---	--

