Statistical Methodology	
For the in vivo assessments of airway remodeling and fibrosis (bronchodilator reversibility on $^{129}\text{XeMRI}$), we will compare biomarkers of fibrosis (e.g., trichrome or percent elastic fiber staining) between BD types (fixed and reversible airway segments) both within and between obese asthma groups (early onset, late onset and non-asthma control) using a repeated measures two-way ANOVA with appropriate distributional assumption. Main effects of BD type, obese asthma group and their interaction will be evaluated with repeating BD type within subject (random effect) with compound symmetry variance structure. If significant main effect differences are found, pairwise comparisons between BD types and obese asthma groups will be done using Tukey's post-hoc test. Assuming a 50% decrease in fibrosis between BD fixed and reversible types, a sample size of 10 per group provides our study with $\geq 80\%$ power to detect an effect size of 0.53 within and 0.60 between groups, where effect size (f) is the size of the mean differences relative to the standard deviation and assumed correlation (ρ) within group of 0.30. A p-value < 0.05 will be considered statistically significant and all analyses will be performed using SAS version 9.4 or higher (SAS Institute, Inc., Cary, NC). Blinding to conditions and tissue sources will occur across the experimental design. In particular, tissues samples (post-BD fixed and BD reversible tissue based on region) will be blinded to the individual performing the experiments and the individual assays. The key for the tissue samples will be maintained by the program statistician and un-blinding will occur during data analysis by the statistician. The statistical models and analyses that are planned for the primary and secondary outcomes assume that the data are missing-at-random (MAR).
 
Because likelihood-based methods will be applied, MAR data still yield valid estimates. Although not expected, if it appears that the MAR assumption is not reasonable, then non-ignorable statistical analyses, such as shared parameter modeling (Albert '19, Gottfredson '14), will be applied.

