All subjects enrolled will undergo bronchoscopy with endobronchial biopsy, brushings and bronchoalveolar lavage (BAL) and blood serum collection. Six endobronchial biopsies and brushings per airway segment will be performed under direct visualization. Biopsy locations will be ^{129}Xe MRI-guided to airway regions of BD fixed and BD reversible defects. Two endobronchial biopsy specimens per airway segment will be fixed in 4% paraformaldehyde and embedded in paraffin. Two or three specimens per airway segment will be used for airway fibroblast culture. Epithelial cells harvested from airway brushes will be grown on air liquid interface for cell culture assays and airway epithelial cell RNA

We will determine airway fibroblast phenotype (i.e. myofibroblast differentiation) in persistent MRI defects post-BD using several methods:

- 1) Airway fibroblasts will be cultured from fresh airway biopsy pieces following Ingram *et al* (34). Immuno-cytochemistry will be performed on cells at passage 0 cultured on collagen-coated chamber slides to determine reactivity with antibodies specific for myofibroblast markers (alpha smooth muscle

actin (α SMA) and amine oxidase, copper containing 3 (AOC3) (77) as well as the fibroblast markers, Fibroblast specific protein-1 (FSP-1) and vimentin, and an epithelial cell marker, E-cadherin.

- 2) Total RNA and protein lysates will be isolated from cells grown at air liquid at Passage 0. Western blotting and quantitative RT-PCR will be used to confirm protein and mRNA expression of α SMA (29) and AOC3 in myofibroblasts, and to rule out expression of epithelial cell protein, E-cadherin.
- 3) To control for cell culture artifacts, fresh airway biopsy tissue will be digested with *ethylenediaminetetraacetic acid disodium* (EDTA) and we will perform fluorescence-activated cell sorting (FACS) for AOC3+ myofibroblasts and AOC3- fibroblasts. Cells will be fixed and stained with anti-vimentin and α SMA to confirm fibroblast and myofibroblast phenotype.

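### Non-asthma controls are crossed with the fixed-versus-reversible segment factor although they may lack one or both segment types; the contrast belongs in the asthma groups, with power restated by complete asthma pairs

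*Combined protocol and SAP*

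**What the plan says.** The model appears in the synopsis (Statistical Methodology) and again under Data Analysis & Statistical Considerations. Fibrosis markers are compared between fixed and reversible segments, within and between "obese asthma groups (early onset, late onset and non-asthma control) using a repeated measures two-way ANOVA". Main effects of BD type and group and their interaction are tested, with BD type repeated within participant under compound symmetry. Ten per group is said to give at least 80% "power to detect an effect size of 0.53 within and 0.60 between groups", with a correlation of 0.30. The synopsis adds that the planned models "assume that the data are missing-at-random (MAR"), with shared parameter modelling as the fallback.

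Other sections determine who can supply the two segment types:

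- Synopsis, Number of Subjects: 15–20 participants in each asthma group and "10 non-asthma obese controls who demonstrate no evidence of atopy or bronchodilator responsiveness". Subject Recruitment and Screening anticipates 40 asthma participants in all.
- Synopsis, criteria for non-asthmatic controls: FEV1 above 80% of predicted and negative methacholine and oscillometry tests are required; "12% or greater bronchodilator response (BDR) in FEV1 to albuterol at Visit 0" is among the exclusions.
- Subject Recruitment and Screening: the imaging review is to "identify segmental persistent post-BD ventilatory defects in obese asthmatics". Controls are not mentioned at that step.
- Bronchoscopy and Clinical Phenotyping: every enrolled participant has a bronchoscopy, and biopsies are "MRI-guided to airway regions of BD fixed and BD reversible defects". The bronchoscopy procedure text gives the same sampling sites.

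No section says which segment is taken, or how it is labelled, when a participant lacks a fixed or a reversible defect.

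**The concern.** A 3 × 2 model with BD type as the repeated factor needs data in all six cells. People chosen for having no airway response to a bronchodilator are the least likely to have a defect that reverses with one, and they may have no persistent defect either. Two outcomes are then possible.

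- **A control cell is empty.** Its mean and the 2-df group-by-type interaction cannot be estimated.
- **Normal control airway is labelled fixed or reversible.** Both control cells then hold the same kind of tissue, and the BD-type main effect averages a real difference in asthma with none in controls.

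The hypothesis under Aim 1 concerns fixed versus reversible defects in obese asthma, so either outcome weakens the test that matters most. An asthma participant with only one defect type raises a related question: is the absent type missing data, or a quantity that does not exist for that person?

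**Working it through.** **Inputs from the plan.** f = 0.53 within and 0.60 between; 10 per group in 3 groups (N = 30); 2 BD types; correlation 0.30; alpha 0.05. Planned enrolment is 15–20 per asthma group plus 10 controls. The mean and SD behind the assumed 50% decrease are not given, so f cannot be derived from it.

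**1. Reproducing the stated power.** Noncentral F with λ = N f² and denominator df = N − number of groups. For the within test, f is then the mean paired difference divided by the SD of paired differences.

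- Within: λ = 30 × 0.53² = 8.43, df 1 and 27, power 0.799.
- Between: λ = 30 × 0.60² = 10.80, df 2 and 27, power 0.800.

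Both figures land on 80%, and only with all 30 participants counted, so the 10 controls are included as complete pairs. The alternative reading takes f relative to the raw SD and applies the correlation separately: λ = 8.43 × 2/(1 − 0.30) = 24.1, power 0.997 within. On that reading 0.53 would not be the effect detectable at 80%, so λ = N f² is used below.

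**2. No control pairs** (two asthma groups, denominator df = pairs − 2):

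| Asthma pairs | λ | Power, f = 0.53 |
|---|---|---|
| 20 | 5.62 | 0.61 |
| 30 | 8.43 | 0.80 |
| 40 | 11.24 | 0.90 |

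**3. Controls supply two segments that do not differ.** Assumption: f = 0.53 in both asthma groups and 0 in controls.

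- Equal group weights: λ = (2/3 × 0.53)² ÷ [(1/9) × Σ(1/n)].
- Sample-size weights: λ = N × [0.53 × (asthma n)/N]².

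| Early/late/control | Equal weights: λ, power | Sample-size weights: λ, power |
|---|---|---|
| 10/10/10 | 3.75, 0.46 | 3.75, 0.46 |
| 15/15/10 | 4.82, 0.57 | 6.32, 0.69 |
| 20/20/10 | 5.62, 0.64 | 8.99, 0.84 |

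The plan does not say which weighting applies.

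**4. Some asthma participants lack one type** (10%, 20%, 30% assumed; asthma-only contrast):

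- 30 enrolled: 27, 24, 21 pairs; power 0.75, 0.70, 0.63.
- 40 enrolled: 36, 32, 28 pairs; power 0.87, 0.83, 0.77.

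**5. Single-type participants in the mixed model.** This was simulated with a REML random-intercept model under stated assumptions: 40 asthma participants, correlation 0.30, true difference zero, and the type present linked to the person's own level by a logistic slope of 1 or 2. With 10–20% single-type participants the bias was about 0.02–0.05 SD and type I error about 4–7%. With 50% the bias was about 0.1–0.2 SD and type I error about 7–13%. The complete-pair contrast was unbiased, at about 5%. The documents give neither the single-type fraction nor the strength of the link.

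**The case against.** **Enrolment exceeds the power text.** A reader might infer that the study lacks 80% power. The documents do not support that. With 15–20 per asthma group and both types in each participant, an asthma-only contrast has 0.80–0.90 with no control pairs; 0.61 applies only if each asthma group stops at 10. Under the raw-SD reading of f, power stays high even at 20 pairs (0.966). What stands is that the analysis as written is not the asthma-only contrast, and that 30 pairs leave no margin.

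**Controls may have regional defects.** A reader might infer that the control cells will be empty. That is an inference too far. The eligibility tests are whole-lung measures, and the background section itself says such tests lack sensitivity to regional change and that xenon MRI shows defects despite normal spirometry, though in asthmatics. The control defect frequency is simply unknown. A coding rule is still needed whatever it is.

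**The mixed model accepts incomplete pairs.** True: not every participant must supply both types. Only a cell that is empty across the whole group blocks estimation.

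**MAR may be adequate.** A reader might infer that the MAR assumption fails. Absence that depends on group or on the MRI reading depends on observed data and does not by itself violate MAR. Bias requires the type present to track the person's underlying remodelling, which is the situation a shared parameter model addresses, and the synopsis names that fallback. Neither approach, however, supplies information for a cell in which nobody has data.

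**Conclusion.** The point holds in a limited form. The plan tests its main tissue contrast, and the interaction, partly in a group that may not have the segments being contrasted, and it has no rule for that case. The consequences are conditional: a cell and the 2-df interaction that cannot be estimated if no control has one of the types, or dilution if control segments are labelled but do not differ. Under dilution, power at planned enrolment runs from 0.57 to 0.84 according to numbers and weighting, against 0.80–0.90 for complete asthma pairs alone.

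These figures rest on λ = N f², which is the convention that reproduces both of the plan's effect sizes, and on an assumed zero difference in controls. The single-type bias is assumption-based and small unless single-type participants are common. The design is sound and planned enrolment can carry the test. This is a correction worth making before unblinding, not grounds to call the 80% claim or the MAR assumption false.

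**What to change.** 1. Test fixed versus reversible, and its interaction with early or late onset (1 df), in the asthma groups only.
2. Enter controls as a separate *no defect* reference for the between-group comparison, not crossed with BD type. Code any segment without a defect as *no defect*, never as fixed or reversible, and state this rule in both statistical sections and where segment selection is described.
3. Restate within-participant power by complete asthma pairs (20: 0.61; 30: 0.80; 40: 0.90), with the range for 10–30% lacking one type: 0.75–0.63 from 30 enrolled, 0.87–0.77 from 40. Give the mean and SD behind the 50% decrease.
4. State that a segment type a person does not have is not missing data. Apply the MAR text to lost or failed specimens, and report the complete-pair contrast.

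**Cost.** This is wording in the statistical sections plus one line on segment coding. Single-type participants leave the paired contrast: if half of 40 were single-type, 20 pairs would remain and power would be 0.61. The power quoted at 10 per group also becomes less favourable.
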